5.1.1.2 Adverse Events

Missing and/or incomplete dates/times for AEs will be imputed in a manner resulting in the earliest onset or the longest duration during the treatment period, taking into account that the start date/time should not be after the stop date/time i.e. missing start dates will be imputed as the first day of the month/first month of the year and missing stop dates will be imputed as the last day of the month/last day of the year, while ensuring that the start date/time is not after the stop date/time. Stop dates/times will not be imputed if the AE is ongoing.

The imputation method will only be used to determine treatment emergence, and imputed dates/times will not be presented in AE outputs.

A worst-case approach will be followed in the event of missing severity or causality data. If the severity is missing, 'Severe' will be imputed. If causality data is missing, 'Yes' will be imputed for the question 'Related to Study Drug?'.

5.1.1.3 Concomitant Medication

Missing concomitant medication dates will be handled in a similar fashion as described for AEs in Section [5.1.1.2](#).

5.1.2 Day Numbering

The first day of treatment in the treatment period (Day 1) will be taken from 'Date of first dose of IMP in Treatment Period' on the Randomization CRF.

Any days prior to Day 1 will be numbered relative to this day and calculated as:

Date – (Date of Day 1)

to give Day -1, -2, -3 etc.

Any days post Day 1 will be calculated as:

Date - (Date of Day 1) + 1

5.1.3 Definitions

5.1.3.1 Baseline

For clinic visit-based endpoints, baseline is defined as the last non-missing record or measure collected prior to the first dose of IMP in the treatment period.

5.1.3.2 Last Visit

Last visit for LOCF based analyses of efficacy endpoints assessed at clinic visits is defined as the last scheduled visit (not including the safety follow-up visit) at which a participant's last evaluation is performed.

5.1.3.3 Placebo Run-in Period

The placebo run-in period is defined as Day -14 to Day -1

5.1.3.4 Treatment Period

The treatment period is defined as Day 1 to Day 85

5.1.4 Covariates

Region strata will be defined as follows:

- North America: Participants who participate in the United States of America will be pooled together;
- Europe: All participants who participate in European countries (Poland, Serbia and Spain) will be pooled together.

Sex strata will be defined as Stratum 1: Male; Stratum 2: Female.

These covariates will be applied to the efficacy analyses and a number of exploratory analyses as outlined in Sections [5.5.2](#) and [5.6](#) respectively.

5.2 Analysis Sets and Protocol Deviations

5.2.1 Full Analysis Set

All participants who were randomized at Visit 3 and received at least 1 dose of IMP in the treatment period will be included and analyzed according to their randomized treatment arm. This analysis set will be the primary analysis set for all efficacy endpoints.

5.2.2 Safety Analysis Set

All participants who received at least one dose of IMP in the treatment period will be included and analyzed according to the treatment received. Only participants for whom it has been confirmed that they did not take any IMP in the treatment period will be excluded from this safety analysis set. This analysis set will be used to report the safety data.

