PP Per protocol

PRN Packaging reference number

PVD Pharmacovigilance Department

QTcF QT interval with Fridericia correction

RNA Ribonucleic acid

RTSM Randomization and Trial Supply Management

SAE Serious adverse event
SAP Statistical analysis plan

SCI-PANSS Structured Clinical Interview Positive and Negative Symptoms

Scale

SOC System organ class

SUSAR Suspected unexpected serious adverse reaction

SQLS Schizophrenia Quality of Life Scale

TBL Total bilirubin

TD Tardive dyskinesia

TEAE Treatment-emergent adverse event

THC Δ^9 -tetrahydrocannabinol

TRH Thyrotropin-releasing hormone

ULN Upper limit of normal

US United States

WOCBP Women of childbearing potential

Confidential Page 26 of 104

EudraCT Number: 2019-003369-16 Clinical Protocol Global V3, 23Mar2021

Definition of Terms

Term	Definition
Day 1	The day a participant first receives investigational medicinal product during the treatment period in this trial.
End of trial	Last participant last visit or last contact, whichever occurs last.
Enrolled participant	Any participant who has provided written informed consent to take part in the trial.
International normalized ratio	A calculation made to standardize prothrombin time.
Investigational medicinal product	Term used to describe both investigational active product and reference therapy (placebo).
Investigator	Trial principal investigator or a formally delegated trial physician.
QT interval	A measure of the time between the start of the Q wave and the end of the T wave in the heart's electrical cycle.

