13.3 Analysis Sets

Study Code: GWAP19030 EudraCT Number: 2019-003369-16 Clinical Protocol Global V3, 23Mar2021

[figure not shown]
The following analysis sets will be used for the statistical analysis:

Full Analysis Set

- All participants who are randomized and receive at least 1 dose of IMP in the trial will be included and analyzed according to their randomized treatment arm.
- The full analysis set (FAS) is the primary analysis set for all efficacy endpoints.

[figure not shown]
Safety Analysis Set

• All participants who receive at least 1 dose of IMP in the trial will be included and analyzed according to the treatment received. Only participants for whom it has been confirmed that they did not take any IMP will be excluded from this safety analysis set. This analysis set will be used to report the safety data.

Confidential Page 78 of 104

Study Code: GWAP19030 EudraCT Number: 2019-003369-16 Clinical Protocol Global V3, 23Mar2021

Analysis sets will be identified prior to the unblinding of the trial data.

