- h. An ECG will be performed after 5 minutes in a supine position, if possible. The ECGs should be done in triplicate at screening and baseline to ensure that QTcF < 450 msec (males)/ < 470 msec (females). Any subsequent ECG should be done once and should be repeated 2 times in cases where withdrawal criteria are met (QTcF ≥ 500 msec).
- i. To include HIV, hepatitis B, and hepatitis C.
- j. Plasma concentrations of the background antipsychotic medications will be assessed at Visit 1 and predose relative to the administration of IMP at Visit 4 and Visit 7.
 - CBD and its major circulating metabolites will be assessed at Visit 1 and relative to the administration of IMP at Visits 4 and 7. A PK sample will be collected before the participant's morning dose of IMP and within 12 hours (-3/+6 hours) since last IMP dose (Visit 4 and Visit 7). Following collection, the IMP will be administered with a meal of at least 300 kcal to be provided. At Visit 1, only a baseline PK sample will be collected. At Visit 4 and Visit 7, samples to determine concentrations of CBD and its major circulating metabolites will be collected pre- and postdose, relative to IMP, at a timepoint between 2 to 3 hours. Thereafter optional PK sampling may be collected at postdose time points between 4 to 6 hours and 8 to 10 hours.
- k. A drug screen test (urine) will include alcohol, amphetamines (including ecstasy), barbiturates, benzodiazepines, cocaine, methadone, opiates, and THC. THC will be blinded from Visit 3 to the end of the trial.
- 1. Assessment to be conducted prior to dosing of any regular medication prescribed for the management of extrapyramidal side effects (e.g., anticholinergics, beta-blockers etc.).
- m. Every effort should be made to include informant information in the PANSS assessment through administration of the Informant Questionnaire PANSS. If contact with a participant's informant cannot be made within 3-day window from the date of the study visit, either by phone or in person, then the informant interview should not be considered a barrier to visit progression.
- n. IMP is to be taken orally b.i.d., (e.g., morning and evening) preferably within 30 minutes of a meal using the syringe(s) provided. Participants will be asked to return all IMP (used and unused) at each relevant visit. The first dose of IMP at Visit 2 should be taken at the site.

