Listing 16.2.4.2	Baseline Characteristics	Safety Analysis Set
Listing 16.2.4.3	Psychiatric History	Safety Analysis Set
Listing 16.2.4.4	Significant Non-Psychiatric Medical or Surgical History	Safety Analysis Set
Listing 16.2.4.5	Concomitant Antipsychotic Medications	Safety Analysis Set
Listing 16.2.4.6	Other Concomitant Medications	Safety Analysis Set
Listing 16.2.5.1	Treatment Compliance	Safety Analysis Set
Listing 16.2.6.1	PANSS Syndromes	Full Analysis Set
Listing 16.2.6.2	PANSS Individual Syndrome Responses	Full Analysis Set
Listing 16.2.6.3	PANSS Total Score and Subscale Scores	Full Analysis Set
Listing 16.2.6.4	CGI-S and CGI-I	Full Analysis Set
Listing 16.2.6.5	PANSS Marder Factors Scores	Full Analysis Set
Listing 16.2.6.6	BACS Verbal Memory and Verbal Fluency	Full Analysis Set
Listing 16.2.6.7	BACS Composite and Domain Scores	Full Analysis Set
Listing 16.2.6.8	Multidimensional Psychological Questionnaires	Safety Analysis Set
Listing 16.2.6.9	Plasma Concentrations	Safety Analysis Set
Listing 16.2.6.10	Plasma Concentrations of Concomitant Antipsychotic Medications	Safety Analysis Set
Listing 16.2.7.1	Treatment Emergent Adverse Events	Safety Analysis Set
Listing 16.2.7.2	Pre-Treatment Adverse Events	Safety Analysis Set
Listing 16.2.7.3	Participants Experiencing Treatment Emergent Adverse Events by System Organ Class and Preferred term	Safety Analysis Set
Listing 16.2.7.4	Serious Adverse Events	Safety Analysis Set
Listing 16.2.8.1	Laboratory Parameters	Safety Analysis Set
Listing 16.2.8.2	Abnormal Laboratory Parameters by Participant	Safety Analysis Set
Listing 16.2.8.3	Abnormal Laboratory Parameters by Parameter	Safety Analysis Set

Listing Number	Title	Analysis Set
Listing 16.2.8.4	Laboratory Comments	Safety Analysis Set
Listing 16.2.8.5	Laboratory Liver Parameters	Safety Analysis Set
Listing 16.2.8.6	Laboratory Reference Ranges and Toxicity Limits	Safety Analysis Set
Listing 16.2.9.1	Vital Signs – Blood Pressures	Safety Analysis Set
Listing 16.2.9.2	Vital Signs – Heart Rate, Respiratory Rate and Temperature	Safety Analysis Set
Listing 16.2.9.3	Vital Signs – Height, Weight, Waist Circumference and BMI	Safety Analysis Set
Listing 16.2.9.4	Potentially Clinically Significant Changes from Baseline for Vital Signs	Safety Analysis Set
Listing 16.2.10.1	ECG Data – Part 1	Safety Analysis Set
Listing 16.2.10.2	ECG Data – Part 2	Safety Analysis Set
Listing 16.2.10.3	Mealtimes	Safety Analysis Set
Listing 16.2.10.4	Physical Examination	Safety Analysis Set

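### The SAP safety set leaves out people dosed only in the placebo run-in, so their AEs and SAEs reach no named AE or SAE output

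*SAP*

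**What the plan says.** Protocol 13.3 sets the safety population by any dosing: "All participants who receive at least 1 dose of IMP in the trial will be included and analyzed according to the treatment received". Its only ground for exclusion is equally broad: "Only participants for whom it has been confirmed that they did not take any IMP will be excluded from this safety analysis set".

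The protocol's Definition of Terms counts placebo as IMP ("Term used to describe both investigational active product and reference therapy (placebo"). Protocol Appendix 1, in the footnote on dosing, places the first dose at the start of the run-in: "The first dose of IMP at Visit 2 should be taken at the site".

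SAP 5.2.2 adds a period restriction to both sentences. Inclusion reads "All participants who received at least one dose of IMP in the treatment period will be included and analyzed according to the treatment received", and exclusion reads "Only participants for whom it has been confirmed that they did not take any IMP in the treatment period will be excluded". SAP 5.1.3.4 sets the treatment period at Day 1 to Day 85, and SAP 5.1.3.3 sets the run-in at Day -14 to Day -1. Of the restricted set, SAP 5.2.2 then says: "This analysis set will be used to report the safety data".

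**The concern.** The run-in is each participant's first exposure to trial product. The placebo vehicle contains sesame oil and ethanol (Protocol 5.2). AEs are collected throughout the run-in, and events after the first IMP dose may be judged related to IMP, since Protocol 12.5 rules out causality only for events that start before that dose.

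The design expects some people to be dosed in the run-in and then not proceed, because several eligibility rules operate between Visits 2 and 3. If every AE and SAE output is tied to treatment-period dosing, a serious event in one of these people is collected but has no place in the planned tables and listings. The SAP would also have moved away from the protocol's safety population without saying so.

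**Working it through.** The documents give no figure to reproduce on this point. The check compares text, then sizes the group under stated assumptions.

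**1. Who belongs to each set**

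| Participant | Protocol 13.3, as written | SAP 5.2.2 |
|---|---|---|
| Dosed in the run-in and in the treatment period | In | In |
| Dosed in the run-in, not randomised at Visit 3 | In | Out |
| Dosed in the run-in, randomised at Visit 3, never dosed afterwards | In | Out |

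**2. Whether the events are collected.** Protocol 12.1.1 and 12.6 collect AEs from after screening to Visit 8, and the Appendix 1 schedule marks AE review at Visit 2 and Visit 3. Run-in events are therefore in the database.

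**3. Which outputs could show them**

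| Output | Population or content | Reaches run-in-only participants as AE data? |
|---|---|---|
| AE and SAE tables, 14.3.2.1 to 14.3.5.8, including fatal TEAEs | Safety Analysis Set | No |
| Listings 16.2.7.1 and 16.2.7.3 (TEAEs) | Safety Analysis Set | No |
| Listing 16.2.7.2, "Pre-Treatment Adverse Events" | Safety Analysis Set | No |
| Listing 16.2.7.4 (SAEs) | Safety Analysis Set | No |
| Table 14.1.1 (disposition) | All screened; SAP 5.4.1 gives counts and reasons for run-in failure | No event data |
| Listing 16.2.1.1 (screen failures) | All screen failures; may or may not cover run-in failures | No event data specified |

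SAP 5.7.2 counts an AE as treatment-emergent only from the first dose in the treatment period. Run-in AEs therefore fall to Listing 16.2.7.2, or to 16.2.7.4 if serious. For people who were later dosed in the treatment period, those two listings cover the run-in events. The gap is confined to the second and third rows of the first table.

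**4. Whether the plan closes the gap elsewhere.** SAP 5.3 says all data are to be listed, but no listing named in Table 10 does this for AEs in run-in-only participants. The amendment table in SAP section 7 has no entry, and the visible text neither states nor explains the change from Protocol 13.3.

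**5. How many people.** The documents do not give the number of run-in failures. Inputs: 80 randomised (SAP 3.2), taken as randomised at Visit 3 and dosed; every run-in entrant dosed at Visit 2; and an assumed failure fraction f. Run-in-only participants = 80/(1 − f) − 80.

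- f = 5%: 80/0.95 − 80 = 4.2
- f = 10%: 80/0.90 − 80 = 8.9
- f = 20%: 80/0.80 − 80 = 20.0
- f = 30%: 80/0.70 − 80 = 34.3

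SAP 3.2 uses the word randomised for both the run-in and the treatment period. If the 80 were run-in entrants, the count would be 80 × f, which is 4 at 5% and 24 at 30%, within the same range. These figures count people, not events. No AE or SAE rate for the run-in is given, so the number of missing events may be zero.

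**The case against.** **The SAP clarifies the protocol rather than narrowing it.** Protocol 13.3 uses the same loose reference to dosing in the trial for the full analysis set. Participants are randomised at both Visit 2 and Visit 3, so a literal reading would put run-in failures into the efficacy population, where they have no double-blind arm. SAP 5.2.1 and 5.2.2 add the same qualifier to both sets. This argument stands for the comparative tables, where the treatment-period set is sensible. It does not settle listings meant to show pre-treatment and serious events, and the protocol's exclusion sentence for the safety set carries no period restriction.

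**SAP 5.3 governs, and Appendix 4 is unreliable.** Appendix 4 does contain clerical errors, such as repeated table numbers and a broken reference. That makes the conflict more likely an oversight than a decision. It remains a conflict, and programming to Table 10 would drop these people.

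**SAEs are handled elsewhere.** Protocol 12.3 requires eCRF entry within 24 hours, with automatic notification to pharmacovigilance. This stands: safety surveillance is not in question, and the SAP list need not define everything in the study report.

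**Redaction.** Text is hidden between SAP 5.5.2.6 and 5.7.2 and after 5.8.1. A statement of the change there cannot be ruled out, so the point is limited to the visible text.

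**A stronger reading to avoid.** A reader might infer that the people most likely to have a run-in SAE are the ones systematically removed, through hospital admission or suicidality. The documents do not show this. Criterion 6.1.5 covers the 12 weeks before screening, and the one-month window in 6.2.5 also refers to screening, although its wording on any history of suicidal behaviour might be read more widely. The suicidality rule in Protocol section 10 applies in the treatment period. Criterion 6.2.12 leaves room for discretion but is not specific. What clearly operates over the run-in or at Visit 3 is the PANSS-T change rule (6.2.6), the baseline PANSS-T range (6.1.6), compliance (6.2.8) and the ECG (6.2.15). Marked worsening can therefore bar a participant, but a change of 20% or more in either direction does so, and improvers are lost too.

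**Conclusion.** The point holds as a moderate gap in the completeness of safety reporting. As written, people dosed in the run-in but never in the treatment period belong to the protocol's safety set, fall outside the SAP's, and have no named AE or SAE output. The visible SAP text does not record the difference, and Table 10 conflicts with SAP 5.3.

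The size is about 4 to 34 people, on assumed run-in failure rates of 5% to 30%; the number of events is unknown. Some selectivity is plausible through the PANSS-T rules but is not established.

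A reader might also infer that the safety comparison of drug with placebo is biased. It is not: everyone affected took single-blind placebo only, and no comparative table changes.

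**What to change.** - Keep the treatment-period safety set for all comparative tables.
- Run Listings 16.2.7.2 and 16.2.7.4, including any deaths, on all participants who took any IMP, run-in placebo included. Label those who never received treatment-period IMP as placebo run-in only.
- State in SAP 5.2.2 that the set differs from Protocol 13.3 and why, and bring the population column of Table 10 into line with SAP 5.3.

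The cost is one population flag applied to two listings and a few sentences of SAP text. No new data are needed, and no comparative result changes.

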5.3 Listings

All data will be listed and ordered by site, treatment, participant number and, where appropriate, chronological order of assessment. Listings will be created for each of the subsequent sections of the SAP.

Visit date need not be included on all of the listings, but day numbers will be included, where appropriate.

Other derived variables (e.g. changes from baseline values) that are calculated for analysis purposes or to aid interpretation of the data will be added to the listings as appropriate.

5.4 Demographic Data and Participant Characteristics

5.4.1 Participant Disposition

Participant disposition will be summarized using standard summary statistics for all screened participants. The number screened, number of screen failures, reasons for failures, number randomized to the placebo run-in period, number of placebo run-in failures, reasons for failure and number randomized to the treatment period, withdrawals and reasons for withdrawals will be included.

5.4.2 Analysis Sets

Participants included in the safety and full analysis sets and participants excluded together with reasons for exclusion will be summarized by absolute counts (n) and percentages (%).

5.4.3 Demographic Data and Baseline Characteristics

The following demographic data will be summarized by treatment group and overall for the full analysis sets:

- Age (years);
- Sex;
- Race;
- Ethnic origin
- Country;
- Region (United States, Europe);
- Weight at baseline (kg);
- Height at baseline (cm);
- Waist circumference (cm);
- Body mass index at baseline (kg/m²).

Age will be calculated as:

$$(\text{Date of screening} - \text{date of birth} + 1) \div 365.25.$$

The following baseline cannabis use data taken from the 'Cannabis Use Survey' CRF page will be summarized by treatment group and overall for the safety analysis sets:

- Age of first use (years).
- Duration since first regular use (years).
- Currently using cannabis (yes/no).
- Regularly using cannabis (yes/no).
- Most common route of current use (smoked, vaped, oral).

5.4.4 Psychiatric History

The following psychiatric history data will be listed only:

- Date of first diagnosis of schizophrenia.
- Date of most recent relapse or acute exacerbation of schizophrenia.

All recorded comorbid psychiatric disorder history will be coded using Version 24.1 of the Medical Dictionary for Regulatory Activities (MedDRA).

The number of participants with comorbid psychiatric disorder history by system organ class, and preferred term, will be summarized by absolute counts (n) and percentages (%) for the safety analysis sets. Percentages will be calculated based on the number of participants in the specific treatment arm. Two tables will be produced, one including any events classified as resolved at screening, and the other including all current conditions.

5.4.5 Medical History

All recorded relevant or significant medical history or current conditions reported other than psychiatric disorders on the 'medical history' CRF page will be coded and summarized using the same method outlined in Section [5.4.4](#).

5.5 Efficacy Analysis

5.5.1 General Approach

The efficacy analyses will use the FAS. No formal hypothesis test will be performed due to early termination of the study (see Section 3.2). Instead, the point estimates and 95% CI for the effects will be presented for efficacy parameters of interest. However, p-values will be presented for flagging purposes and not to be used for results interpretation.

5.5.2 Efficacy Endpoints

The efficacy of GWP42003-P versus placebo after 12 weeks of treatment is measured by the following efficacy endpoints which will be compared between treatment groups:

- Mean change from baseline to Week 12 in the following:
 - Structured Clinical Interview Positive and Negative Symptoms Scale (SCI-PANSS) total (PANSS-T) score
 - PANSS positive subscale (PANSS-P) score
 - PANSS negative subscale (PANSS-N) score
 - PANSS general subscale (PANSS-G) score
 - Clinical Global Impression of Severity (CGI-S) score
- Score at Week 12 in the Clinical Global Impression of Improvement (CGI-I)

5.5.2.1 PANSS-T

The SCI-PANSS is a medical scale used for measuring symptom severity of participants with schizophrenia or related psychotic disorder. The name refers to the 2 types of symptoms in schizophrenia, as defined by the American Psychiatric Association: positive symptoms, which refer to an excess or distortion of normal functions (e.g., hallucinations and delusions), and negative symptoms, which represent a diminution or loss of normal functions.

It is a 30-item rating instrument that assesses the positive and negative symptoms of schizophrenia as well as symptoms of general psychopathology. Individual items are rated on a 7-point scale, where 1 = absent and 7 = extreme. A PANSS-T score is derived from the sum of the 30 items and the total score ranges from 30 to 210. Missing data will be handled as specified in Section [5.1.1.1](#). This scale will be measured at each assessment visit, with the primary time point of interest being Day 85.

The change from baseline in PANSS-T score will be analyzed using a mixed-effects repeated measures (MMRM) model. An MMRM model will be fitted to the change in PANSS-T score at each visit and will include stratification factors (sex [male or female] and region [North America or Europe]), associated baseline, visit, treatment arm, visit by treatment arm interaction and visit by associated baseline interaction as fixed effects and

visit repeated within each participant as a repeated effect. For the analysis of the PANSS-T score; baseline PANSS-P, baseline PANSS-N and PANSS-G will be included in the model as fixed effects for the associated baseline instead of baseline PANSS-T.

The PROC MIXED procedure in SAS will be utilized to perform the analysis. An unstructured covariance matrix will be used to estimate the variance-covariance structure within participants across time points. If convergence is not obtained, or model fit is not adequate then other covariance structures will be explored in the following order until the model converges:

- Toeplitz
- First-order autoregressive
- Compound Symmetry

This order is specified according to a decreasing number of covariance parameters in the structure. The primary analysis will use the first covariance structure converging to the best fit. If a structured covariance is used, the sandwich estimator for the covariance estimation will be used by specifying the EMPIRICAL options in the PROC MIXED procedure in SAS with the aim to deal with model misspecification of the covariance matrix.

The least squares (LS) mean estimates for each treatment arm at each visit, along with the standard error and 95% confidence intervals (CIs) will be presented. In addition, the estimate of the treatment difference at each visit will be presented along with standard errors of the difference and associated 95% CIs. The primary comparison is the estimate of the difference at Day 85.

For participants who complete the trial, regardless of whether IMP is prematurely discontinued or not, the visit effect used in the analysis will correspond to the associated score at each trial visit. However, participants who withdraw from the trial are required to complete the procedures for End of Treatment at the time of withdrawal. For these participants, their End of Treatment data will be assigned to the nearest post-baseline visit (for which the assessment is scheduled to be performed), based on the trial day of the visit.

The values including change from baseline for PANSS-T will be summarized using standard summary statistics for the full analysis set.

